5.4.2.5.2. Analysis Methods

The number and percentage of participants who achieve a response will be summarized at each time point during the double-blind treatment phase by intervention group. The analysis will be performed on observed as well as imputed data (participants with missing values will be imputed as non-responders).

A Chi-square test will be used to test the difference between JNJ-55308942 mg once daily and placebo for response rate at each time point. A 2-sided 80% CI for the intervention difference will be calculated based on the Wald statistic. The point estimate and 2-sided 80% CI will be provided for the relative risk of response.

Response rate will be plotted over time by intervention group.

The cumulative response rate, defined as the percentage of participants experiencing at least a given value of percent reduction from baseline to Week 6 in the MADRS total score, will be presented graphically for observed data.

5.4.2.6. Remission Based on MADRS Total Score

5.4.2.6.1. Definition

A participant is defined as a remitter at a given time point if the MADRS total score is ≤ 12 at that time point. Participants who do not meet such a criterion will be considered as non-remitters. Imputation of missing remission status is presented in Section 5.1.3.

5.4.2.6.2. Analysis Methods

The number and percentage of participants who achieve remission will be summarized at each time point during the double-blind treatment phase by intervention group. The analysis will be

performed on observed as well as imputed data (participants with missing values will be imputed as non-remitters).

A Chi-square test will be used to test the difference between JNJ-55308942 mg once daily and placebo for remission rate at each time point. A 2-sided 80% CI for the intervention difference will be calculated based on the Wald statistic. The point estimate and 2-sided 80% CI will be provided for the relative risk of remission.

The remission rate will be plotted over time by intervention group.

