5.1.3. Imputation of Efficacy

Imputation for missing data will include the following methods (Table 3).

Table 3: Imputation of Missing Efficacy Data

Imputation	Text
Multiple Imputation (MI)	1) Copy Reference
method	2) Delta Adjustment.
Non-Responder	Participants with missing values will be imputed as non-responders.
Non-Remitter	Participants with missing values will be imputed as non-remitters.

Imputation of total scores will apply only to the MADRS. Imputation of the MADRS total score will be performed only when 1 item score is missing. If 2 or more items are missing, the total score will be left missing. The total score will be imputed by calculating the sum of the scores of the non-missing items and multiplying it by the ratio of the maximum possible number of items (i.e., 10) to the number of non-missing items (i.e., 9).

For all other efficacy scales where multiple items are summed to create a total score, if any item of the scale is missing on one visit, the total score for that scale at that visit will be left missing.

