5.3.2.1. Analysis Methods

5.3.2.1.1. Primary Analysis

The primary efficacy analysis will be performed utilizing the hypothetical estimand defined above. The change from baseline in MADRS total score will be compared between the JNJ-55308942 mg once daily group and the placebo group at Week 6 in a mixed-effects model for repeated measures (MMRM), with time, intervention (placebo or JNJ-55308942), BD type (I or II), country, P2RX7 GoF SNP mutation genotype (homozygous or heterozygous), concomitant medication status (no mood stabilizer or antipsychotic, a mood stabilizer alone, an antipsychotic alone, or a combination of a mood stabilizer and an antipsychotic), and time-by-intervention interaction as factors, with baseline MADRS total score as a continuous covariate. Data after treatment discontinuation will be considered missing. The within-subject covariance between visits will be estimated via an unstructured variance-covariance matrix. In case of convergence problems, alternative variance-covariance structures will be attempted in the following order, with the first structure that converges being used in the analysis: heterogeneous Toeplitz, standard Toeplitz, and first order autoregressive. Kenward-Roger approximation will be used to estimate the denominator degrees of freedom. Sandwich estimator will be used to address the potential misspecification of the covariance matrix when a structured covariance matrix is used due to the convergence problem with the unstructured covariance matrix.

The comparison of JNJ-55308942 versus placebo will be performed using the appropriate contrasts directly from the MMRM analysis. A 2-sided 80% confidence interval (CI) for the difference in least squares means will be presented over time. A 1-sided p-value will be calculated at Week 6. Least square means of change from baseline (+/- SE) will be presented graphically over time.

Descriptive statistics of the actual values and the change from baseline to each postbaseline time point will be presented for MADRS total score by intervention group.

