5.4.1.1.2. Analysis Methods

Descriptive statistics of the actual values at Baseline, Week 6, and the change from baseline to Week 6 will be presented for SHAPS total score by intervention group.

An analysis of covariance (ANCOVA) model will be used to test the difference of change from baseline at Week 6 in SHAPS total score between JNJ-55308942 mg once daily and placebo. The model will include intervention (placebo or JNJ-55308942), BD type (I or II), country, P2RX7 GoF SNP mutation genotype (homozygous or heterozygous), and concomitant medication status (no mood stabilizer or antipsychotic, a mood stabilizer alone, an antipsychotic alone, or a combination of a mood stabilizer and an antipsychotic) as factors, and baseline SHAPS total score as a covariate. Comparison between JNJ-55308942 mg once daily and placebo will be performed using appropriate contrast. Difference of least square means and 2-sided 80% CI will

be presented. Least square means of change from baseline (+/- SE) to Week 6 will be presented graphically.

Frequency distributions of the SHAPS individual items will be provided at each assessment time point.

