5.4.2.2.2. Analysis Methods

Descriptive statistics of the actual values and the change from baseline at each post-baseline time point will be presented for PROMIS - Ability to Participate in Social Roles and Activities total T-score, total raw score, and individual items by intervention group and visit.

The change from baseline in the PROMIS - Ability to Participate in Social Roles and Activities total T-score will be analyzed using a similar MMRM as described in Section 5.3.2.1.1, with the covariate "baseline MADRS total score" changed to "baseline PROMIS - Ability to Participate in Social Roles and Activities total T-score". Comparison between JNJ-55308942 mg once daily and placebo will be performed using the appropriate contrasts. Difference in least square means and 2-sided 80% CI will be presented over time. Least square means of change from baseline (+/-SE) for PROMIS T-score will be presented graphically over time.

Frequency distributions of the individual items of the PROMIS - Ability to Participate in Social Roles and Activities will be provided at each assessment time point.

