5.4.2.3.2. Analysis Methods

Descriptive statistics of the actual values and the change from baseline to each post-baseline time point will be presented for the PHQ-9 total score and individual items by intervention group.

The analysis for changes from baseline in PHQ-9 total score at each week will be carried out using a similar MMRM as described in Section 5.3.2.1.1 for the primary efficacy endpoint, with the covariate "baseline total MADRS score" changed to "baseline PHQ-9 total score". Comparison between JNJ-55308942 mg once daily and placebo will be performed using the appropriate contrasts. Least square means of change from baseline (+/- SE) for the PHQ-9 total score will be presented graphically over time.

Frequency distributions of the PHQ-9 individual items will be provided at each assessment time point.

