5.4.2.4.2. Analysis Methods

Descriptive statistics of the actual values and the change from baseline at weeks 2, 4, and 6 will be presented for the GAD-7 total score and individual items by intervention group for observed case data.

The analyses for changes from baseline in GAD-7 total score at weeks 2, 4, and 6 will be carried out using a similar MMRM as described in Section 5.3.2.1.1 for the primary efficacy endpoint, with the covariate "baseline total MADRS score" changed to "baseline GAD-7 total score". Comparison between JNJ-55308942 mg once daily and placebo will be performed using the appropriate contrasts. Least square means of change from baseline (+/- SE) for the GAD-7 total score will be presented graphically over time.

Frequency distributions of the GAD-7 individual items will be provided at each assessment time point.

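### Remission is compared without adjusting for baseline MADRS, so a chance difference in starting severity passes straight into it, while every modelled efficacy comparison adjusts for its own baseline

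*SAP*

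**What the plan says.** SAP section 5.4.2.6.1 fixes an absolute cut-off: "A participant is defined as a remitter at a given time point if the MADRS total score is" 12 or less. Section 5.4.2.6.2 compares the arms by a chi-square test "for remission rate at each time point. A 2-sided 80% CI for the intervention difference will be calculated based on the Wald statistic", and adds a relative risk with its own 80% CI. It does this on observed data and on imputed data, for which section 5.1.3 says: "Participants with missing values will be imputed as non-remitters". No covariate, stratum or adjusted supporting analysis is named.

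The models elsewhere in the SAP all carry a baseline term:

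- Primary MMRM (5.3.2.1.1): "with baseline MADRS total score as a continuous covariate". The subgroup models in 5.4.1.2.2 reuse it.
- SHAPS ANCOVA (5.4.1.1.2): "and baseline SHAPS total score as a covariate".
- PROMIS, PHQ-9 and GAD-7 MMRMs (5.4.2.2.2, 5.4.2.3.2, 5.4.2.4.2): "baseline PROMIS - Ability to Participate in Social Roles and Activities total T-score", "baseline PHQ-9 total score" and "baseline GAD-7 total score" respectively.

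Protocol section 4.1 bases entry on the HDRS17 rather than the MADRS. SAP section 1.2.1 stratifies randomisation by BD type, country, genotype and concomitant medication. Table 8 of the SAP tabulates baseline MADRS by arm. Protocol section 9.4.1 planned only to summarise remission; the test and intervals were added in the SAP.

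**The concern.** A participant who starts at 25 needs a fall of 13 points to remit; one who starts at 37 needs 25. If one arm starts lower by chance, it will tend to show more remitters for a reason unrelated to the drug. The primary MMRM removes that effect. The remission comparison, built from the same MADRS scores, keeps it.

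The design does not balance baseline MADRS directly, because it is neither an entry threshold nor a stratification factor. Table 8 would reveal an imbalance but not correct for it, and a decision to adjust made after seeing Table 8 would be post hoc.

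The point concerns remission. Response is a percentage change from baseline and is less exposed, unless the Week 6 score follows baseline almost one for one.

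**Working it through.** **The plan's own figure.** The documents give no power for remission. The stated total reproduces: n per arm = 2(1.2816 + 1.2816)² / 0.45² = 64.9, so 65; 65 / 0.80 = 81.25, so 82; 2 × 82 = 164.

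**Inputs from the documents.** 82 per arm, change SD 8.6, difference 3.9, 20% drop-out counted as non-remission (SAP 3 and 5.1.3).

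**Inputs assumed, because the documents do not give them.** Baseline mean 31; baseline SD 4 to 6; a Week 6 score that rises by b = 0.3 to 1.0 per baseline point; placebo mean change −10 to −16.

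**Step 1: how often the arms start apart.** The SE of the baseline difference is SD × √(2/82).

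| Baseline SD | SE | Chance of a gap of 1 point or more in one given direction |
|---|---|---|
| 4 | 0.625 | 5.5% |
| 5 | 0.781 | 10.0% |
| 6 | 0.937 | 14.3% |

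**Step 2: what one point does to the crude remission difference.** Take SD 5, placebo change −13 (Week 6 mean 18) and b = 0.6.

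- Residual variance = 8.6² − (0.6 − 1)² × 25 = 69.96.
- Week 6 SD = √(69.96 + 0.36 × 25) = 8.886.
- z for a score of 12 or less = (12.5 − 18) / 8.886 = −0.619, with normal density 0.3294 and tail area 0.268.
- Shift per point = 0.8 × 0.6 × 0.3294 / 8.886 = 0.0178, or 1.78 percentage points.
- Remission rate = 0.8 × 0.268 = 0.214, so SE = √(2 × 0.214 × 0.786 / 82) = 6.4 points. The shift is 0.28 SE.

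The same formula gives 0.95 points at b = 0.3 and 2.75 at b = 1.0. Simulation gives 0.97, 1.78 and 2.76.

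**Step 3: simulation.** There were 54 scenarios of 40,000 trials each, with simple 1:1 allocation and no strata. The crude method is the Pearson chi-square. The adjusted method is a logistic model with treatment and baseline, giving a standardised risk difference with a delta-method SE. Both are read at one-sided 0.10, which matches the 80% CI; the SAP states no level for this test. Middle case (SD 5, placebo change −13):

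| | b = 0.3 | b = 0.6 | b = 1.0 |
|---|---|---|---|
| No effect, active at least 1 point lower: crude / adjusted error | 0.152 / 0.114 | 0.180 / 0.104 | 0.230 / 0.106 |
| No effect, active at least 1 point higher: crude / adjusted error | 0.075 / 0.106 | 0.048 / 0.106 | 0.027 / 0.104 |
| Difference 3.9, all trials: crude / adjusted power | 0.777 / 0.783 | 0.714 / 0.733 | 0.646 / 0.685 |
| Difference 3.9, active at least 1 point higher: crude / adjusted power | 0.713 / 0.775 | 0.585 / 0.741 | 0.424 / 0.682 |

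**Over all scenarios.**

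- Shift per point: 0.7 to 3.3 percentage points crude, under 0.1 adjusted.
- Error over all trials: 9.9 to 10.6% crude, 10.0 to 10.6% adjusted.
- Error with the active arm at least 1 point lower: 14 to 24% crude, 10 to 12% adjusted.
- Error with the active arm at least 1 point higher: 2 to 8% crude, 9 to 11% adjusted.
- Overall power: 60 to 80% crude, 65 to 81% adjusted.
- Coverage of the 80% CI in trials with a 1-point imbalance: 72 to 81% crude, 77 to 80% adjusted.

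**Response, for contrast.** The crude shift per point is +0.6 to +0.8 at b = 0.3, −0.2 to −0.4 at b = 0.6 and −1.5 to −1.9 at b = 1.0.

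**The case against.** The strongest reply is that nothing here is an error. A chi-square test for a secondary binary endpoint is a recognised choice, its error over all randomisations is nominal, and no success rule rests on remission. The striking error rates come from the minority of trials with a gap of at least 1 point. At baseline SD 5 and placebo change −13, 79 to 80% of trials fall inside that gap, and there the crude error is 9.3 to 10.8%. Over all trials the two methods reach the same decision in 95 to 98% (no effect) or 90 to 97% (difference 3.9). All of that stands and limits the weight of the point.

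The size also depends on assumed inputs, with the upper ends coming mainly from b = 1.0. That stands too; at b = 0.3 the overall power gain is under 1 point. The HDRS17 floor at entry may narrow the spread of baseline MADRS, and the simulation ignores any balance that the four strata provide. Both could reduce the effect, but neither balances MADRS directly.

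Remission is not the only crude comparison: response gets the same test, and the forest plot in SAP 5.4.2.7 uses unadjusted mean changes. That is so, but remission is the one with an absolute cut-off. Adjusting at Week 6 only would also leave the earlier visits crude, which is tolerable because the secondary objective is set at Week 6.

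What the reply does not answer is the single realised trial. If the arms start apart, the direction of the distortion is known in advance, and the means to remove it is already collected.

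**Conclusion.** The concern holds as an optional improvement. The planned remission comparison is valid on average but leaves in a chance baseline MADRS difference that the primary analysis removes. A 1-point gap moves it by 0.7 to 3.3 percentage points against a standard error of 4.9 to 7.5. The average gain from adjusting is small (0 to 5 points of power). The main benefit is protection in the roughly 5 to 15% of trials, in each direction, where the gap reaches 1 point. These sizes rest on the assumed baseline mean and SD, slope and placebo change. The direction needs only that a higher starting score tends to mean a higher Week 6 score. The primary conclusion is unaffected.

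**What to change.** Before unblinding, amend SAP 5.4.2.6.2 for Week 6:

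- Make the main remission comparison, on the FAS with missing values counted as non-remission, a logistic model with treatment and continuous baseline MADRS.
- Report the standardised risk difference and relative risk (predicted risk averaged over all FAS participants under each treatment) with 2-sided 80% CIs by the delta method, on the log scale for the relative risk.
- Take the p-value from the same standardised risk difference and SE, so that it agrees with the CI.
- Keep the crude percentages, chi-square and Wald results at all visits, and the observed-case version, as supportive.

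The four randomisation factors are not needed for this purpose. If they are added, pool sparse levels by a rule fixed before unblinding. Response can stay as planned or take the same model for consistency.

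The cost is SAP wording and one standard procedure. No new data are needed, and nobody is lost, because FAS membership already requires a baseline MADRS. The fit is stable: 27 to 63 remitters on average with a difference of 3.9, for three parameters. The mean standardised difference is within 0.03 points of the mean crude one. There are two downsides. One more remission result has to be reported, and when the active arm happens to start at least 1 point lower the adjusted result is less favourable than the crude one (power 64 to 80% against 79 to 86%).

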5.4.2.7. Additional MADRS Subgroup Analysis

Changes in MADRS total score to Week 6 from baseline, will be assessed in subgroups for concomitant medication status (no mood stabilizer or antipsychotic, a mood stabilizer alone, an antipsychotic alone, or a combination of a mood stabilizer and an antipsychotic) and country. Descriptive statistics of the actual values and change from baseline at each postbaseline time point in the MADRS total score will be presented by intervention group for the subgroups. Mean changes from baseline (+/- SE) will be presented graphically over time. A forest plot summarizing the differences of mean changes and 2-sided 80% CI between JNJ-55308942 mg once daily and placebo at Week 6 in the subgroups will be presented. The change from baseline in the MADRS total score will be analyzed using the same MMRM described in Section 5.3.2.1.1 for each subgroup when feasible.

5.5. Exploratory Endpoint(s) Analysis

5.5.1. Self-Assessment of Well-Being (SAWB)

5.5.1.1. Definition

The SAWB questionnaire is a multiple-item self-report questionnaire designed to provide additional information regarding the participant's subjective experience while taking study intervention. This is an internal Janssen questionnaire, and the questions will be asked to the participant daily by the Q1.6 app during the double-blind treatment phase. The SAWB questionnaire has a total of 11 questions. The first 8 questions monitor the participant's manic symptoms, pattern of sleep, energy level, social activities, and concentration level. Each question is answered with a visual analog scale (VAS) between 0 and 100. Question 9 asks the participant's subjective experience of overall depression level since study start with 3 possible answers: a) improved, b) not changed, or c) worsened. If the participant answers "improved", Question 10 will be asked to assess how much depression has improved (slightly improved, much improved, or very much improved). If the participant answers "worsened" to Question 9, Question 11 will be asked to assess how much depression has worsened (slightly worse, much worse, or very much worse). The 8 VAS questions will be rotated with 2 questions being asked on a single day. The remaining questions will be asked weekly. The Q1.6 app will send an alert to the investigator when the participant has indicated that her/his depression is "much worse" or "very much worse".

5.5.1.2. **Analysis Methods**

Analysis of the SAWB data will be based on the safety analysis set.

Actual values will be averaged by study week for each of the 8 VAS items. Descriptive statistics of the weekly average of each of the 8 VAS items will be presented by intervention group over time. Mean (+/- SE) of the weekly average of each of the 8 VAS items will be presented graphically over time.

A frequency distribution at each time point by intervention group will be provided for Questions 9 to 11. The number and percentage of participants with a reply that her/his depression is 'much worse' or 'very much worse' will be summarized by intervention group. A listing of participants with a reply that her/his depression is 'much worse' or 'very much worse' will be provided.

5.6. Safety Analyses

All safety analyses will be based on the safety analysis set based on actual intervention received, unless otherwise specified.

5.6.1. **Extent of Exposure**

Duration of study intervention and total number of capsules taken will be summarized by intervention group using descriptive statistics.

Study intervention duration is defined as (date of last dose of study intervention – date of first dose of study intervention) +1.

Total number of capsules taken will be calculated based on drug accountability data.

In case a medication packet is not returned by a participant or the drug accountability data is missing, the actual number of capsules taken may be inferred based on Digital Healthy Assessment app data if available.

5.6.1.1. **Intervention Compliance**

Compliance will be summarized descriptively for each intervention.

The percent compliance will be categorized and the number and percentage of participants in each category will be summarized by intervention group.

Compliance will be calculated as follows:

Compliance (%) = (actual number of capsules taken/total number of capsules supposed to be taken) x100.

5.6.2. **Adverse Events**

The verbatim terms used in the CRF by investigators to identify adverse events (AEs) will be coded using the Medical Dictionary for Regulatory Activities (MedDRA). Any AE occurring at or after the initial administration of study intervention through the day of the last dose plus 30 days

CONFIDENTIAL – FOIA Exemptions Apply in U.S.

is considered to be treatment-emergent. If the event occurs on the day of the initial administration of study intervention, and either event time or time of administration is missing, then the event will be assumed to be treatment-emergent. If the event date is recorded as partial or completely missing, then the event will be considered to be treatment-emergent unless it is known to be prior to the first administration of study intervention based on the partial onset date or resolution date. All reported treatment-emergent adverse events (TEAEs) will be included in the analysis. For each AE, the number and percentage of participants who experience at least 1 occurrence of the given event will be summarized by intervention group.

Summary tables will be provided for:

- Overall summary of TEAEs, including any TEAEs, serious TEAEs, TEAEs leading to discontinuation of study intervention, related TEAEs, and TEAEs by worst severity
- TEAEs by system organ class and preferred term
- Treatment-emergent serious adverse events (SAEs) by system organ class and preferred term
- TEAEs leading to discontinuation of study intervention by system organ class and preferred term
- TEAEs by system organ class, preferred term, and worst severity
- TEAEs by system organ class, preferred term, and relationship to study intervention.

In addition to the summary tables, listings will be provided for participants who had:

- AEs
- SAEs
- AEs leading to discontinuation of study intervention

A listing of participants who died will be provided.

